## 4 STUDY DESIGN

### 4.1 OVERALL DESIGN

This is a pragmatic, open-label, single-center, randomized phase 2 pilot clinical trial for superiority of a multi-faceted anemia prevention and treatment strategy assessing the impact of the intervention on hemoglobin concentrations and functional outcomes after hospitalization. We hypothesize that the multifaceted anemia intervention will increase hemoglobin concentrations and will improve multi-faceted functional recovery after hospitalization when compared to standard care.

Patients satisfying inclusion/exclusion criteria, or their legal proxies, will be approached by trained study coordinators for written informed consent. Participants will be randomized 1:1 to active intervention vs. standard care using a stratified permuted block design by anemia etiology (iron-responsive or not) and ICU admission indication (surgical vs. non-surgical). The intervention arm is multi-faceted with 3 primary components: 1) **Optimized phlebotomy**, defined by minimal volume draws (i.e. 0.1-2 ml vs. standard 3-10 ml per laboratory order) and closed-loop blood sampling (eliminates 10 ml waste volume per draw), all performed by a dedicated phlebotomy team independent from the treatment team; 2) **Decision support aids**, including visual and electronic alerts reminding the care team to minimize non-essential laboratory testing and mitigate patient-specific bleeding risk (e.g. stress ulcer prophylaxis in high-risk patients); and 3) **Pharmacologic anemia treatment** (given immediately following enrollment when hemoglobin first observed <10 g/dL) targeted to 2 broad groups: 1) anemias responsive to iron supplementation alone (i.e. acute blood loss, true iron deficiency [i.e. ferritin <100 ng/ml, transferrin saturation < 20%]), and 2) anemias requiring erythropoietic stimulation (e.g. anemia of inflammation, anemia of renal disease). Etiology of anemia will be determined immediately prior to randomization upon review of laboratory values (i.e. iron studies) and clinical history (i.e. admission diagnoses, surgery/acute blood loss) with treatment decisions adjudicated pre-randomization by the PI or Co-I's. Subjects then randomized to the intervention arm will receive pharmacologic anemia treatment in accordance with their anemia etiology. Patients with anemias responsive to iron supplementation will receive a single total dose infusion (1000 mg) of intravenous (IV) iron dextran. Patients with anemias requiring erythropoietic stimulation will receive a single dose of 40,000 units of subcutaneous EPO, which will be immediately preceded by 1000 mg of IV iron dextran to replenish usable iron stores if the ferritin level is < 1000 ng/ml. All patients randomized to the intervention group will receive

either IV iron, EPO, or both. Targeted pharmacologic anemia therapies are being employed given that anemia in acute blood loss/post-surgery and true iron deficiency is iron-restricted and responds to iron supplementation alone; hence, the potential harms of EPO (e.g. thrombosis) likely outweigh benefits.

#### Outcome assessment:

In-person outcome assessments will occur at 1 month and 3 months post-hospitalization, with investigators and outcome assessors blinded to treatment allocation. The **primary outcome** will be the mean difference in hemoglobin between groups at 1 month. Differences in hemoglobin concentrations will also be assessed at ICU discharge, hospital discharge, and 3 month follow-up. **Secondary outcomes** will include changes in phlebotomy practice (i.e. number of draws, total volume of draws) during hospitalization and functional outcomes at 1 and 3 months, employing the NHLBI-funded Core Outcome Measurement Set (COMS) for survivors of critical illness (aim 2b). This includes validated measures of physical function (6MWD, ADL survey), cognition (Montreal Cognitive Assessment Blind), mental health (Hospital Anxiety and Depression Scale, Impact of Events Scale-Revised), and quality of life (EQ-5D). Additionally, as an optional study component, we will solicit patients to wear an activity monitor (Actigraph) on their wrist for 4 consecutive days at 1 and 3-months, from which we will capture daily step counts and energy expenditure measurements. We will also assess several Epic-embedded patient-reported outcomes (i.e. PROMIS) with multidimensional computerized adaptive testing (i.e. PROMIS CAT), laying the groundwork for validation in critical illness research. Differences in RBC transfusion rates will be assessed through 3 month follow-up. We will also assess hospital readmissions and mortality through 12-months post-hospitalization. Research samples obtained will be stored for potential biomarker assessment (i.e. hepcidin, IL-6, C-reactive protein) for future mechanistic studies on anemia development and recovery in critical illness survivors.

#### Sample size estimation:

Power/sample size are calculated to detect a difference in the primary endpoint of hemoglobin at 1 month follow-up. Preliminary data show mean (standard deviation) hemoglobin levels of 10.8 (1.5) g/dL at 1 month among 636 patients with similar inclusion/exclusion criteria receiving standard care. A total sample size of 74 (37 per group) provides 80% power to detect 1.0 g/dL improvement using a two-sample unequal variances t-test with 2-sided alpha of 0.05 to compare 1 month hemoglobin between randomized arms. Actual power is expected to be higher under the analysis approach, adjusting for pre-randomization prognostic variables to reduce residual variation. If adjustment variables account for 25% of the variation in 1 month hemoglobin ( $R^2$  for relationship between pre-randomization adjustment variables and outcome = 0.25), the sample size of 37 per group provides 90% power to detect a 1.0 g/dL improvement using analysis of covariance with 2-sided alpha of 0.05. While the analysis uses a linear mixed-effects model (LMM), power is not appreciably different for the LMM as compared to the unequal variances t-test or ANCOVA described here. Given expected dropout of up to 25% (death, loss to follow-up) resulting in loss of information, 100 subjects will be enrolled.

#### Statistical considerations:

The primary outcome is hemoglobin measured repeatedly on subjects at ICU discharge, hospital discharge, and 1 month and 3 months. The longitudinal trajectory of hemoglobin will be analyzed with a LMM. The primary parameter of interest is a treatment group by time interaction to estimate the effect of treatment at each follow up time-point. The treatment effect on 1 month hemoglobin is the primary outcome; other time-points will reflect secondary outcomes. As the functional form of hemoglobin over time is unknown, a discrete time representation will be used. The model will adjust for pre-randomization hemoglobin, age, sex, anemia etiology, and medical vs surgical ICU setting to reduce residual variation and improve precision of the estimated treatment effect.

Dropout or non-response including skipped study visit and death represent two forms of missing data. Dropout or non-response unrelated to death at ICU discharge and hospital discharge is expected to be negligible but could occur with

withdrawal of consent. We assume dropout (unrelated to death) while in the ICU is missing completely at random (MCAR); patients withdrawing consent prior to observation of hemoglobin outcome at ICU discharge will be excluded from the analysis. Those dropping out after ICU discharge are assumed missing at random (MAR) with missingness possibly related to adjustment covariates, arm, or prior observed hemoglobin values. Analyses using LMM assume dropout, nonresponse, or skipped visits are MAR.

We anticipate up to 10% ICU mortality (despite exclusion of those not expected to survive hospitalization); such subjects will not have observed hemoglobin outcomes. We also anticipate additional post-ICU discharge mortality. In the primary analysis, we assume missing data due to death is MAR. Those with ICU mortality will have ICU discharge hemoglobin multiply imputed under the MAR assumption. Thereafter, LMMs assume additional missing data at other times are MAR. In secondary approaches to the analysis of hemoglobin, we use a worst-case imputation approach, to impute hemoglobins as the worst possible outcome following death. After imputation, if residuals are not reasonably normally distributed, a generalized linear mixed effects proportional odds model will be used or individual timepoints may be assessed by Wilcoxon rank-sum test without covariate adjustment. A similar approach using proportional odds models or Wilcoxon rank-sum test will apply to functional outcomes which are not expected to satisfy regression assumptions including normality of residuals. Similar approaches assuming MAR and MNAR will be applied to missing functional outcome data.

#### 4.2 SCIENTIFIC RATIONALE FOR STUDY DESIGN

*This is a randomized parallel arm clinical trial comparing the multifaceted anemia intervention against control (standard care).* The control group will receive standard care without an active placebo for several reasons: 1) the multifaceted nature of the study intervention makes it difficult to design a placebo for each unique intervention element, particularly clinical decision support and optimized phlebotomy); 2) the expenses associated with administering a placebo for pharmacologic agents (i.e. iron, EPO) are considerable and would not be possible through the NIH K-23 funding mechanism; and 3) this is a pilot trial which will inform a larger, multi-center definitive clinical trial in which we would have the resources available for placebo administration of pharmacologic therapies. Superiority will be assessed as the goal is to improve anemia in the critically ill, given that the problem of anemia is extremely prevalent in the ICU, rather than to prove non-inferiority against standard care.

#### 4.3 JUSTIFICATION FOR DOSE

IV iron given as a single total dose infusion of 1000 mg of IV low molecular weight iron dextran, which provides complete restoration of usable iron for >4 weeks and is the most commonly used dose in clinical practice for patients with iron deficiency. For anemias requiring erythropoietic stimulation, EPO will be given as a single 40,000 unit dose after ensuring restoration of iron stores, a strategy that has resulted in sustained hemoglobin improvement and is widely used in anemia clinics. A single EPO dose carries a lower risk for thrombotic complications than repeat dosing, which is particularly relevant in the critically ill. Defining optimal treatment dosing and duration remains a priority for future research.

#### 4.4 END OF STUDY DEFINITION

A participant is considered to have completed the study if they have completed all phases of the study including the last visit shown in the Schedule of Activities (SoA), Section 1.3. Data on mortality and hospital readmission will be extracted at 12-months post-hospitalization for each patient by review of the electronic medical record.

### 5 STUDY POPULATION

#### 5.1 INCLUSION CRITERIA

To be eligible to participate in this study, an individual must meet all the following criteria:

1. Provision of signed and dated informed consent form (may be completed by legal proxies for those patients unable to provide consent, i.e. sedation/intubation)
2. Stated willingness to comply with all study procedures and availability for the duration of the study, including follow-up assessments
3. Male or female, age  $\geq$  18 years
4. Current ICU admission at Mayo Clinic Rochester
5. Current ICU duration  $\leq$  7 days
6. Patients embedded in the local or regional Mayo Clinic Health System to facilitate post-hospitalization outcome assessment
7. Moderate-to-severe anemia (i.e. hemoglobin concentration  $< 10$  g/dL) at the time of enrollment, with the hemoglobin concentration assessed no more than 24 hours prior to enrollment. If RBC transfusion has been administered between the qualifying hemoglobin assessment and enrollment, a repeat hemoglobin will be required prior to enrollment to ensure that it remains  $< 10$  g/dL.

## 5.2 EXCLUSION CRITERIA

An individual who meets any of the following criteria will be excluded from participation in this study:

1. IV iron or any ESA use (i.e. darbepoetin, Aranesp, erythropoietin, Epojen, Procrit, Retacrit) within 30 days of enrollment. Oral iron is permitted (e.g. oral iron supplements, multivitamin with iron)
2. Severe anemia prior to hospitalization (i.e. hemoglobin consistently  $< 9$  g/dL in the 90 days prior to admission). If hemoglobin is not available or if hemoglobin is  $\geq 9$  g/dL at any time within 90 days prior to enrollment, then this criterion is not met, and the patient may be enrolled
3. Known allergic reactions to IV iron or any EPO agent
4. Inability to complete outcome assessments (i.e. not expected to survive hospitalization, unable to make follow-up appointments, non-ambulatory status preceding hospitalization, dementia or other severe cognitive impairment, visual impairment i.e. blind or legally blind, non-English speaking)
5. Pregnancy or breastfeeding at time of enrollment given unclear safety of EPO
6. Inability to receive pharmacologic venous thromboembolic prophylaxis except in patients with acute blood loss anemia (i.e. recent surgery or gastrointestinal bleeding, extracranial bleeding)
7. Active or suspected thrombosis (i.e. DVT, pulmonary embolism, acute arterial thrombus) within 3 months except in patients with acute blood loss anemia (i.e. recent surgery, gastrointestinal bleeding, extracranial bleeding)
8. Uncontrolled sepsis (i.e. lack of definitive source control and/or  $< 48$  hours of appropriate antimicrobial therapy)
9. Having received  $\geq 10$  units of allogeneic RBCs in the 48 hours before enrollment
10. Acute coronary syndrome (STEMI or NSTEMI) or ischemic stroke within 3 months except in patients with acute blood loss anemia (i.e. recent surgery, gastrointestinal bleeding, extracranial bleeding)
11. Weight less than 40 kg
12. Concerns with study enrollment expressed by the clinical team

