
Regarding EPO, several actions are being taken to mitigate risk: 1) excluding patients with relative contraindications to EPO therapy (e.g. pregnancy, active thrombosis, an inability to receive VTE pharmacoprophylaxis, active myocardial ischemia, poorly controlled hypertension, recent stroke); 2) tailoring pharmacotherapy to anemia etiology, such that EPO is not administered to patients that are likely to mount an appropriate erythropoietic response with iron therapy alone; and 3) providing only a single dose of EPO therapy for those receiving this therapy. Of note, the optimal dosing of EPO is unknown in the critically ill, though clinical trials in surgical patients have shown that a single dose of EPO results in sustained hemoglobin improvement. All adverse events will be closely evaluated by study personnel as outlined in the data safety monitoring plan. Similar to iron, EPO will be administered by critical care nurses in accordance with institutional medical administration protocols. Iron will be co-administered immediately prior to EPO to ensure adequate iron stores for EPO-induced augmentation of bone marrow erythropoiesis. Patients will be continuously monitored at the time of administration for immediate adverse effects (e.g. cutaneous reactions, hypertension, dizziness, nausea). Those without immediate reaction will be observed clinically for 1 hour post-infusion for the

development of delayed reactions with blood pressure measurements at least every 15 minutes, continuous pulse oximetry, and telemetry. Those experiencing infusion reactions will be observed for longer times as dictated by the severity of the reaction.

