## 6 STUDY INTERVENTION

### 6.1 STUDY INTERVENTION(S) ADMINISTRATION

#### 6.1.1 STUDY INTERVENTION DESCRIPTION

The intervention arm is multi-faceted with 3 primary components:

- 1) **Optimized phlebotomy**, defined by minimal volume draws (i.e. 0.1-2 ml vs. standard 3-10 ml per laboratory order) and closed-loop blood sampling, all performed by a dedicated phlebotomy team independent from the treatment team. This intervention simply requires communication with the phlebotomy team rather than any direct change to patient care.
- 2) **Decision support**. This includes:
  - a. A visual clinical support tool (appendix) urging the clinical team to minimize laboratory assessments and optimize patient bleeding risk. This will be available by the clinical workstations for the ICU team and at the patient's bedside.
  - b. A daily rounding checklist (appendix) accompanied by brief daily discussion (2-minutes) between trained study coordinators and the ICU care team during clinical rounds to reiterate the purpose of the study. The checklist will be available at the clinical workstations for the ICU team.
  - c. Epic direct messages sent twice per day (targeting day and night providers) with the information from the visual support tool to reiterate the purpose of the study.
- 3) **Pharmacologic anemia treatment**. These therapies will be given immediately following enrollment and targeted to 2 broad groups:
  - a. Anemias responsive to iron supplementation alone. This includes patients with anemia secondary to acute blood loss  $\geq$  500 ml and patients with iron deficiency anemia (i.e. ferritin  $<100$  ng/ml or transferrin saturation  $<20\%$ ).
    - Patients with iron-responsive anemias will receive a single total dose infusion (1000 mg) of intravenous (IV) low molecular weight iron dextran (INFeD)
    - This medication is diluted in 500 ml of 0.9% saline. A 25 mg test dose (12.5 ml) is administered over 5 minutes to ensure no immediate hypersensitivity reaction, followed by the completion of the infusion over 1-2 hours (not to exceed 1000 mg/hr). This medication will be given in accordance with Mayo Clinic administration guidelines.

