  - b. Anemias requiring erythropoietic stimulation. This includes anemia not secondary to acute blood loss or iron deficiency (e.g. anemia of inflammation, anemia of renal disease). Etiology will be determined immediately *prior to randomization* upon review of laboratory values (i.e. iron studies) and clinical history (i.e. admission diagnoses, surgery/acute blood loss) with treatment decisions adjudicated pre-randomization by the PI and trial Co-I's should the PI be unavailable.
    - Patients without iron-responsive anemias will receive a single dose of 40,000 units of subcutaneous EPO (Retacrit). For those with ferritin less than 1000 ng/ml they will also receive 1000 mg IV iron prior to EPO administration to replenish usable iron, given that iron will

invariably be mobilized secondary to EPO stimulation. EPO will be given in accordance with Mayo Clinic administration guidelines.

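### Exclusions waived for acute blood loss anemia carry no volume, treatment allocation uses 500 ml, and one narrow group is left with conflicting instructions on EPO

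*Combined protocol and SAP*

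**What the plan says.** Three of the 12 exclusion criteria in 5.2 carry the same exception:

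- Criterion 6: "Inability to receive pharmacologic venous thromboembolic prophylaxis except in patients with acute blood loss anemia (i.e. recent surgery or gastrointestinal bleeding, extracranial bleeding".
- Criterion 7: "Active or suspected thrombosis (i.e. DVT, pulmonary embolism, acute arterial thrombus) within 3 months except in patients with acute blood loss anemia".
- Criterion 10: "Acute coronary syndrome (STEMI or NSTEMI) or ischemic stroke within 3 months except in patients with acute blood loss anemia".

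Each describes the exception by clinical setting (surgery, gastrointestinal or extracranial bleeding) and none states a volume.

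Section 6.1.1 then allocates treatment within the intervention arm. Item 3a reserves the iron-only pathway for acute blood loss of at least "500 ml and patients with iron deficiency anemia", the latter defined by ferritin below 100 ng/ml or TSAT below 20%. Item 3b describes the EPO group: "This includes anemia not secondary to acute blood loss or iron deficiency". Its dosing line says "Patients without iron-responsive anemias will receive a single dose of 40,000 units of subcutaneous EPO (Retacrit". Borderline cases go to adjudication: "treatment decisions adjudicated pre-randomization by the PI and trial Co-I's should the PI be unavailable".

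Section 4.1 lists acute blood loss as iron-responsive with no volume, and says that every intervention patient receives iron, EPO or both. Section 2.3.3 gives as a risk safeguard that "EPO is not administered to patients that are likely to mount an appropriate erythropoietic response with iron therapy alone". It also tabulates inability to receive VTE prophylaxis, thrombosis or myocardial ischemia, and recent stroke as exclusions, with no exception shown.

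**The concern.** The waiver makes sense only if the patients it admits receive iron and not EPO. That link holds if acute blood loss anemia means the same thing when eligibility is decided and when treatment is chosen. As worded, it does not: 5.2 uses a definition with no volume and item 3a uses one with a 500 ml threshold. A patient could be admitted under the first and fall outside the second.

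The patients concerned have a recent thrombosis, acute coronary syndrome or ischemic stroke, or cannot receive VTE prophylaxis. The protocol itself gives these as reasons to avoid EPO. In addition, someone who reads only the risk-benefit section would conclude that no such patients are enrolled.

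**Working it through.** This is a check of wording; the plan gives no figure to reproduce.

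**Step 1: which waived patients does item 3a cover?** Item 3a is met if loss is at least 500 ml, or ferritin is below 100 ng/ml, or TSAT is below 20%. Three two-level factors give 2 × 2 × 2 = 8 combinations. Item 3a fails only when all three conditions fail, which is 1 combination, so 8 − 1 = 7 give iron alone. The one left over is loss under 500 ml, ferritin at least 100 ng/ml and TSAT at least 20%.

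**Step 2: what does the text say about an intervention-arm patient in that cell who was enrolled under a waiver?**

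| Text | Direction |
|---|---|
| 6.1.1 item 3a | Does not cover the patient |
| 6.1.1 item 3b, opening | Not in the EPO group (anemia is from blood loss, any volume) |
| 6.1.1 item 3b, dosing line | EPO, if failing 3a means not iron-responsive |
| 4.1, treatment groups | Iron alone (blood loss, any volume) |
| 4.1, all intervention patients treated | Must receive iron, EPO or both |
| 2.3.3, EPO safeguards and rationale | Iron alone |
| 1.1 Synopsis | EPO group described as anemia of inflammation, so not this patient |

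The patient is outside both 3a and the opening definition of 3b, yet must be treated, and the only dosing line in 6.1.1 that reaches the patient is the one for EPO.

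**Step 3: which readings lead to EPO in that cell?**

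| Eligibility definition | Treatment definition | Result |
|---|---|---|
| No volume | No volume | Iron alone |
| No volume | 500 ml | EPO |
| 500 ml | No volume | Excluded |
| 500 ml | 500 ml | Excluded |

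Using either definition consistently avoids EPO. EPO follows only in the second row, but that row is how 5.2 and item 3a are each literally written.

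**Step 4: section 2.3.3.** The table has 10 rows. Three of them (VTE prophylaxis; thrombosis or myocardial ischemia; stroke) correspond to criteria 6, 7 and 10 and omit the exception. The EPO paragraph in the same section repeats those exclusions, again without it.

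Section 4.1 separates the ferritin and TSAT conditions with a comma, where item 3a says or. This does not enlarge the disputed cell, because 4.1 treats all acute blood loss as iron-responsive, but the two should be worded alike.

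**The case against.** The strongest reply is that the EPO reading takes one line out of its context. The dosing line sits under item 3b, which opens by confining the group to anemia not caused by acute blood loss. On that reading the cell is a gap and not an instruction to give EPO, and 4.1 fills the gap with iron. The same investigators adjudicate etiology before randomization, and they would have to call the anemia blood loss for eligibility and something else for treatment. The waiver is also for anemia caused by blood loss: a trivial bleed that did not cause the low hemoglobin should not open it, so the cell is narrower than a loss under 500 ml suggests. Criterion 12 allows the clinical team to object, and EPO must follow institutional administration guidelines, whose content the protocol does not give. Finally, 2.3.3 is rationale, and 5.2, the operative section, states the exceptions openly.

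Much of this stands. The intent is plain, the cell is small, and the 2.3.3 omission alone would be clerical. It does not remove the contradiction. If smaller losses count as iron-responsive anyway, the 500 ml threshold does no work. Adjudication is a real safeguard, but nothing tells the adjudicator which definition governs, and no sentence in 5.2 or 6.1.1 expressly bars EPO for a patient admitted under a waiver.

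**Conclusion.** The concern holds, as a minor inconsistency of wording with a safety aspect. Under item 3a, 7 of 8 combinations give iron alone and 1 of 8 is in conflict. These are counts of combinations, not probabilities. Only intervention-arm patients enrolled under a waiver can be affected. The documents do not say how often this cell occurs, so no number of patients is claimed. The wording mismatch and the omission in 2.3.3 (3 of 10 table rows) are certain. That any patient would actually receive EPO this way is unlikely, given the stated intent and the adjudication. The conclusion assumes that the waiver can apply to a loss under 500 ml, which the text of 5.2 permits. No effect on the primary analysis is claimed.

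**What to change.** 1. State in 5.2 and 6.1.1 that a patient enrolled under the exception to criterion 6, 7 or 10 must be adjudicated iron-responsive before randomization and must not receive study EPO; otherwise the exclusion applies.
2. Use one definition of acute blood loss anemia in 4.1, 5.2 and 6.1.1 (items 3a and 3b). Whether it keeps the 500 ml threshold is for the investigators and the IRB.
3. Add the exceptions to the table and the EPO paragraph in 2.3.3.

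The cost is a wording amendment through the IRB and one field on the eligibility form, since adjudication already takes place before randomization. A few patients may change treatment pathway or eligibility.
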